Data analysis method	
 
1. Trial data will be summarised using a CONSORT diagram and analyses will be based on intention-to-treat principles.
 
2. Between-group comparisons will be conducted at the end of each phase using ANOVA.
 
3. The primary analyses will examine between-group differences in occupational burnout (OLBI) severity over time (after each of the 3 phases, post-baseline).
 
4. Secondary analyses will involve comparing between-group differences in each of the OLBI burnout dimensions (exhaustion, disengagement), and in measures of subjective well-being and personal goal attainment.
 
5. We will also quantify and report intervention completion / dropout rates, and self-reported days on sickness leave.
 

Study Period	24 months (18 months active study period, plus 6 months analyses and dissemination)

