#### 3.3. Hypotheses

- A) Exposure to the intervention will be associated with significantly lower mean burnout severity by comparison to a waitlist (delayed intervention) control group
- B) After the control group is exposed to the intervention, there will be no significant differences in mean burnout level between the two groups (immediate intervention group, delayed intervention group)
- C) Mean burnout severity for all participants at the end of the 6-month follow-up period will be significantly lower than baseline severity (prior to intervention), but not significantly different to end-of-treatment severity, indicating maintenance of gains

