### 4. Study design

This will be a pragmatic, stepped wedge, open-label, randomised controlled trial. Consenting NHS staff will be randomly assigned to two groups, by a research assistant using a computerized randomization algorithm (applying a simple 1:1 randomization schedule). The study will be carried out in four phases, which are illustrated in Figure 1.

Figure 1. Stepped wedge trial design

Participants in both groups will be asked to complete outcome measures during a pre-intervention baseline assessment (week 0). After the baseline assessment, only participants in group 1 will access an 8-week intervention (controlled phase). Next, group 2 will access the intervention during an 8-week period (full implementation phase). Finally, we will collect further outcome measures 6 months after both groups have completed the intervention (follow-up phase). The outcome measures will be completed continuously at each of the measurement points outlined in the above timeline (weeks 0, 8, 16, 40). All measures will be completed online using an industry-standard survey system (Qualtrics – which automatically sends email reminders to consenting participants), which will be managed by a research assistant.

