##### *Data collection and safeguarding procedures*

- All participants irrespective of group allocation will be asked to complete the primary and secondary measures described above, at four assessment points, as illustrated in Figure 1 (weeks 0, 8, 16, 40). The measures will be gathered by an independent researcher, who is not involved in the intervention. The researcher will use a secure, web-based, data collection system called Qualtrics.

Therefore, all data collection will be in electronic form, using unique participant pseudonyms, which cannot personally identify any of the study participants, or identify their random allocation.

- At the time of attendance at their initial group intervention session, participants will be asked to complete a brief checklist where they will report basic demographics and generic information about their role (see Appendix 3). These paper-based surveys will be entirely anonymous (no names, pseudonyms or identifiers), in order to protect participants' confidentiality. Participants will be asked to deposit their survey into a box, which will be managed by a member of the research team, who will then transcribe the results onto a spreadsheet, which will be safely stored in a secure network drive. The only reason to collect these data is to enable the research team to provide basic aggregated sample characteristics (e.g., mean age and standard deviation, % of people from a minority ethnic group, etc.) This will enable us to assess if the study sample is broadly representative of the wider NHS workforce or not.
- The dataset will be stored in a secure University network drive, only accessible to members of the research team, which is located behind The University of Sheffield Firewall. This will ensure the security and adequate storage of research data, consistent with NHS and academic codes of information governance and data protection.
- All analyses will be carried out at a University site, and data will be held in a restricted-access drive. The study dataset will be held at the University for a minimum of 5 years after the conclusion of the study.

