### 5.2. Primary analysis

Trial data will be summarised using a CONSORT diagram and all analyses will be based on *intention-to-treat* principles. Missing data will be imputed using an expectation-maximization algorithm, prior to conducting formal analyses.

The primary hypothesis test (A) will be based on comparing mean outcome measures between groups at week 8, as shown in Figure 1. Mean OLBI scores will be compared between groups using analysis of covariance (ANCOVA), controlling for baseline severity.

Sensitivity analyses will be performed to assess the robustness of the main findings. This will involve repeating the comparison of means whilst controlling for any potential site-effects (systematic differences in burnout between NHS services), introducing a site variable as a random effect.

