### 5.3. Secondary analyses

ANCOVA (and sensitivity analyses) described above will be repeated at each of the time-points illustrated in Figure 1 (weeks 0, 8, 16, 40), using the OLBI (total score; then separate domain scores), and using the WEMWBS as an outcome, controlling for baseline scores. Outcomes at 6-months follow-up (pooled for both groups) will be compared to outcomes at the baseline assessment, using paired-samples t-tests (or an appropriate non-parametric test depending on the distribution of the data).

We will carry out an exploratory analysis of sickness absence, by comparing the mean number of sickness absence days reported by all participants for the 6 months preceding the start of the study, and the mean sickness absence days reported during the 6-month follow-up period after both groups completed the intervention. This within-group comparison will be carried out using a paired-samples t-test (or an appropriate non-parametric test depending on the distribution of the data).

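### Hypothesis B reads the full implementation phase through a non-significant week-16 difference, which cannot by itself show that Group 2 benefited, and neither group's week 8 to 16 change is estimated

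*Protocol*

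**What the plan says.** Protocol section 4 describes the design: "This will be a pragmatic, stepped wedge, open-label, randomised controlled trial". Group 1 is treated in weeks 0 to 8. For the following phase the protocol says "Next, group 2 will access the intervention during an 8-week period (full implementation phase"). Section 4.4 has every participant measured "at four assessment points, as illustrated in Figure 1 (weeks 0, 8, 16, 40"), so Group 2's last untreated score (week 8) and its end-of-treatment score (week 16) are both collected.

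Section 3.3 states Hypothesis B: "After the control group is exposed to the intervention, there will be no significant differences in mean burnout level between the two groups". No equivalence margin is given.

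The listed OLBI analyses are:
- Section 5.2: "The primary hypothesis test (A) will be based on comparing mean outcome measures between groups at week 8", by ANCOVA controlling for baseline.
- Section 5.3: "ANCOVA (and sensitivity analyses) described above will be repeated at each of the time-points illustrated in Figure 1 (weeks 0, 8, 16, 40"), again between groups and adjusted for baseline.
- Section 5.3: a paired test of week 40 against baseline, with both groups pooled.

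The Synopsis agrees on the between-group approach: "Between-group comparisons will be conducted at the end of each phase using ANOVA".

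**The concern.** Half of the randomised nurses are first treated in weeks 8 to 16. The natural question about that phase is whether Group 2 improved when treated. Hypothesis B asks instead whether the two groups are level at the end of it. They can be level because Group 2 caught up, or because Group 1 slipped back and Group 2 never moved. They can differ because Group 2 did not respond, or because it responded and Group 1 faded.

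To tell these cases apart, one needs each group's change from week 8 to week 16. Neither change is among the listed analyses. The pooled week-40 test spans the whole study and both groups, so it does not supply them. The second half of Hypothesis C, on maintenance from end of treatment, has no matching test in section 5.3.

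At stake is the reading of a secondary hypothesis. The report could present B as upheld, and readers could take that as the effect having recurred in the delayed group, when Group 2 gained nothing. It could also report B as failed when Group 2 gained in full.

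**Working it through.** **Inputs from the protocol (section 5.1).** 67 per group, 80% power, alpha 0.05, a moderate effect with no number attached, 30% dropout.

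**Assumptions.** Moderate means 0.5 SD; SD 1 at each wave; two-sided tests; equal correlation ρ between waves, 0.6 with a range of 0.4 to 0.8; 67 per group observed at weeks 0, 8 and 16.

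**The plan's own figure.** 134 / 0.7 = 191.4, so 192 is reproduced. An effect of 0.5 SD needs 64 per group for 80% power by the two-sample t test; 67 gives 81.9%. So 67 is not matched exactly, but the gap is on the safe side and nothing below depends on it.

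**What the week-16 test sees.** Let *a* be the gain Group 1 still has at week 16 and *b* the gain Group 2 has made. The ANCOVA estimates *b* − *a*, with

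SE = √(2(1 − ρ²)/67) = 0.158, 0.138 and 0.104 SD at ρ = 0.4, 0.6 and 0.8.

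B is satisfied when the result is non-significant:

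P = Φ(1.96 − δ/SE) − Φ(−1.96 − δ/SE), with δ = |*b* − *a*|.

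| State at week 16 | *a* | *b* | δ | B satisfied at ρ = 0.4 / 0.6 / 0.8 |
|---|---|---|---|---|
| Both gain, Group 1 holds | 0.5 | 0.5 | 0 | 95% / 95% / 95% |
| Group 1 fades fully, Group 2 gains nothing | 0 | 0 | 0 | 95% / 95% / 95% |
| No effect in anyone | 0 | 0 | 0 | 95% / 95% / 95% |
| Group 1 keeps half, Group 2 gains in full | 0.25 | 0.5 | 0.25 | 65% / 56% / 33% |
| Group 1 keeps half, Group 2 gains nothing | 0.25 | 0 | 0.25 | 65% / 56% / 33% |
| Group 1 holds, Group 2 gains nothing | 0.5 | 0 | 0.5 | 12% / 5% / 0.2% |
| Group 1 fades fully, Group 2 gains in full | 0 | 0.5 | 0.5 | 12% / 5% / 0.2% |

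Example, row 4 at ρ = 0.6: 0.25/0.138 = 1.81, and Φ(1.96 − 1.81) = 0.56. Simulation of 4,000 trials per scenario gave 64%, 57% and 34% for that row. A separate simulation at ρ = 0, 0.5 and 0.7 gave 94 to 96% for the rows with δ = 0, and 18%, 10% and 2% for the row in which Group 1 holds and Group 2 gains nothing.

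The first two rows cannot be told apart at week 16, nor can rows 4 and 5 by significance alone. An equivalence margin would not separate the first two, because the true difference is zero in both. In the second row Hypothesis A is still positive in about 95% of trials (87 to 99.8%), so A and B would usually both be reported as upheld.

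**What the missing estimates would give.**
- Group 2, week 8 to 16: SE = √(2(1 − ρ)/67) = 0.109 SD at ρ = 0.6, so the 95% CI half-width is 1.96 × 0.109 = 0.21 SD (0.26 to 0.15 over the range). Simulated power for a 0.5 SD gain is 99% (96 to 100%).
- The same change set against Group 2's waiting-period change: SE = √(6(1 − ρ)/67) = 0.189 SD. Simulated power is 74% (56 to 96%).
- Exposure to time trend: if burnout drifted down by an assumed 0.2 SD for reasons unrelated to treatment, 0.2/0.109 = 1.83, and the uncontrolled Group 2 change would show a false gain in about 44% of trials.

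**The case against.** Several points on the other side stand.

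- **The second phase is analysed.** A reader might infer that nothing planned uses it. The documents do not support that: section 5.3 and the Synopsis both plan a week-16 between-group comparison, and the pooled week-40 test includes treated Group 2.
- **The week-16 test can be informative.** A reader might also infer that it gives the same answer whether or not Group 2 responds. That is not generally so. If Group 1 holds its full gain, B is satisfied in about 95% of trials when Group 2 responds and about 5% when it does not (2 to 18% in the simulation at correlations 0.7 to 0).
- **A and B are read together.** If the programme works in nobody, A comes out positive in the beneficial direction in only about 2.5% of trials, so that state rarely yields A and B both upheld. The harmful pairing needs Group 1 to fade and Group 2 not to respond, and no figure in the protocol says how likely that is.
- **The protocol does not itself say that B shows benefit in Group 2.** It only predicts no difference. The misreading is a risk, not a stated claim.
- **The within-group change has its own weakness.** It is open-label and uncontrolled for time, as the 44% figure shows, so it should not displace a randomised comparison.
- **A statistical analysis plan, not shown, may add contrasts.** That answers the missing estimates in part. It does not answer the wording of Hypothesis B, which the protocol fixes.

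What remains is that the week-16 test is informative only if Group 1's gain lasts, and the listed analyses do not check that.

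**Conclusion.** The point holds as a limited one about a secondary hypothesis. A non-significant week-16 difference does not establish that Group 2 benefited, and a significant one does not establish that it failed to. Both depend on Group 1's retention, which the protocol's analyses do not estimate between weeks 8 and 16. With 67 per group, a 0.5 SD effect and correlation 0.6, B is satisfied in about 95% of trials if Group 1 fades fully and Group 2 gains nothing. It is satisfied in only about 57% (64% at correlation 0.4, 34% at 0.8) if Group 2 gains in full and Group 1 loses half. The effect size, the correlations and the degrees of fading are assumptions; the protocol gives none of them. The week-8 primary test is sound on this point and unaffected. The matter should be corrected, but does not threaten the main result.

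**What to change.** In section 5.3, keep the week-16 between-group ANCOVA, report it as a difference with a 95% CI, and state that non-significance will not be taken as support for Hypothesis B.

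Add one repeated-measures model (group by week, all randomised nurses) and report from it, each with a 95% CI:
- Group 2's change from week 8 to week 16;
- Group 2's waiting-period change, week 0 to week 8;
- Group 1's change from week 8 to week 16.

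Restate Hypothesis B in terms of these estimates: burnout in Group 2 is lower at week 16 than at week 8, read beside its own waiting period and beside Group 1's retention. Do the same for WEMWBS.

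The cost is one reworded secondary hypothesis and one extra model on data already collected, with no new visits or participants. The downside is that Group 2's change is within-group and open-label, and the waiting-period comparison removes time trend only in part and with less power (about 74%). It should be labelled secondary and supportive. The week-8 primary test stays as written.

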#### 4.1. Setting and participants

This study will be conducted with registered nurses working in community based services across all four care groups in Rotherham Doncaster and South Humber NHS Foundation Trust (RDaSH). The services provide planned and unplanned home-based care and community clinic-based care for children and adults. The specialist services may include one or more of the following: holistic assessment, case management, treatment and symptom management for acute and chronic conditions, mental health care, medicines administration, palliative care and end of life care, wound care management, and other health and educational interventions.

##### *Inclusion criteria*

- The study participants will be nursing staff currently working in Rotherham Doncaster and South Humber NHS Foundation Trust (RDaSH), either full-time or part-time.
- All participants will be RDaSH employees and hold an active professional registration with the Nursing and Midwifery Council (NMC).
- aged 18+

##### *Exclusion criteria*

- Currently accessing or referred to any concurrent psychological intervention delivered by a professional.
- Nurses that are currently not in active service at the time of recruitment (e.g., on sick leave, maternity leave or suspended for any reason).

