#### 3.2. Secondary Objectives

- To assess if the intervention improves subjective well-being
- To assess if the intervention improves personal goal attainment
- To assess if the intervention reduces sickness absence
- To quantify completion and dropout rates

[figure not shown]

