### *Secondary measures*

The Warwick-Edinburgh Mental Well-being Scale (WEMWBS) is a 14-item questionnaire; each answered on a 1 to 5 Likert scale. Items cover different aspects of eudaimonic and hedonic mental wellbeing and are worded positively. Item scores are summed to produce a total score (range: 14 to 70), where higher scores indicate greater psychological well-being. Psychometric testing has indicated that this measure was valid, reliable and acceptable measure of well-being in adult respondents (Tennant et al., 2007); with good internal consistency (Cronbach's alpha = .89 to .91) and test-retest reliability (.81).

Participants will be asked to report the number of sickness absence days they have had during the 6-month period preceding the start of the study, and will self-report any sickness absence days taken during the active study and observation period.

Participants will also be asked to report basic demographics (age, gender, ethnicity) and generic information about their work setting (adult services, children's services, inpatient vs. outpatient care).

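### Nurses on sick leave are excluded at recruitment but not at follow-up, so the before-after absence comparison tilts towards an increase and can hide a real reduction (minor)

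*Protocol*

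**What the plan says.** Three parts of the protocol bear on this point.

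- **Exclusion criteria (4.1).** These remove "Nurses that are currently not in active service at the time of recruitment (e.g., on sick leave, maternity leave or suspended for any reason".
- **Secondary measures (4.3).** Participants are asked to "report the number of sickness absence days they have had during the 6-month period preceding the start of the study". They also self-report absence during the study and observation period.
- **Secondary analyses (5.3).** The pre-study mean is compared with "the mean sickness absence days reported during the 6-month follow-up period after both groups completed the intervention", over all participants. "This within-group comparison will be carried out using a paired-samples t-test", or a non-parametric equivalent. The section introduces this with "We will carry out an exploratory analysis of sickness absence".

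The analysis serves a listed secondary objective (3.2): "To assess if the intervention reduces sickness absence". It is the only absence analysis that the protocol describes. Section 4 places the measurements at weeks 0, 8, 16 and 40. Section 4.4 asks all participants to complete the measures, whatever their group, and nobody is removed for later sick leave.

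**The concern.** The entry rule selects on the same quantity that 5.3 later compares. A nurse in the middle of a long spell at recruitment cannot enter, so the days of that spell never reach the pre-study total. A nurse in the middle of a long spell during weeks 16 to 40 stays in, and those days count. If the underlying absence rate never changed, the enrolled nurses would still be expected to show more absence per day in follow-up than before the study.

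By follow-up both groups have had the intervention, so no concurrent control can reveal this drift. The before-after change could then look flat, or smaller than it is, even if the intervention reduces absence, and a reader could take that as evidence against it.

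**Working it through.** The protocol states no figure for sickness absence, so there is none to reproduce. The check asks how large the drift would be with no intervention effect.

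**Inputs from the protocol.** Nurses on sick leave at recruitment are excluded (4.1). The pre-study window is six months, taken as 182 days (4.3). Follow-up runs from week 16 to week 40, which is days 112 to 280, or 24 weeks = 168 days (section 4). Completers number 134 (5.1).

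**Assumptions (the protocol gives none).** Absence is stationary at 5% of days. Short spells average 4 days. Long spells average L days and make up a share s of days lost. Spell lengths are geometric. Recruitment and study start are treated as the same day. If recruitment falls a few weeks earlier, the depletion lies on both sides of that date within the window, so it is not smaller.

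**Model.** There are three states: at work, short spell, long spell. The daily chance of starting a short spell is 0.05(1−s)/(4×0.95), and of starting a long spell 0.05s/(L×0.95). The daily chances of returning to work are 1/4 and 1/L. For L = 60 and s = 0.6 the two starting chances are 0.00526 and 0.000526. Let w(k) be the probability of being at work k days from a day at work. The chain is reversible, so w(k) applies both backwards and forwards:

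- pre-study days = sum over k = 1 to 182 of 1 − w(k)
- follow-up days = sum over k = 112 to 279 of 1 − w(k)
- per-day ratio = (follow-up/168) ÷ (pre-study/182)

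| Long spells | Pre-study days (182) | Follow-up days (168) | Per-day ratio | Ratio of raw days | Ratio, 24 v 24 weeks |
|---|---|---|---|---|---|
| none | 8.96 | 8.40 | 1.02 | 0.94 | 1.02 |
| 30 days, 30% | 8.59 | 8.39 | 1.06 | 0.98 | 1.06 |
| 45 days, 50% | 8.00 | 8.32 | 1.13 | 1.04 | 1.14 |
| 60 days, 60% | 7.44 | 8.17 | 1.19 | 1.10 | 1.21 |
| 90 days, 70% (extreme) | 6.46 | 7.70 | 1.29 | 1.19 | 1.32 |

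For example, (8.17/168)/(7.44/182) = 0.0486/0.0409 = 1.19. Without the exclusion the expected days would be 0.05×182 = 9.10 and 0.05×168 = 8.40, a per-day ratio of exactly 1. The excess is therefore due to the entry rule alone. The last column shows that equal windows remove the length difference but not the selection.

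**Masking.** Suppose absence truly falls by 20% (an illustrative figure). The apparent per-day change is 0.8 × ratio − 1: about −15% (0.8×1.058), −10% (0.8×1.127) and −5% (0.8×1.190) in the 30-, 45- and 60-day rows.

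**Second check with a different set-up.** This was a daily simulation of 40,000 nurses with one 4-day short spell a year and 0 to 0.15 long spells a year (mean 60 or 90 days), with and without differences in proneness between nurses. Over two 182-day windows the null ratio ran from 1.03 (short spells only) to about 1.35. With a 24-week follow-up the ratio of raw days was 0.95 to 0.96 with short spells only, and 1.04 to 1.24 with long spells. With 134 completers and 182-day windows, the chance of a significant rise was 3% to 12%, against a nominal 2.5% in that direction.

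**Restricting follow-up to nurses at work at week 40.** With 24-week windows, follow-up days become the sum over k = 112 to 279 of 1 − w(k)w(280−k)/w(280). The null ratio is then 0.999, 0.990 and 0.971 in the 30-, 45- and 60-day rows, and 0.918 in the 90-day row.

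**The case against.** Four objections deserve weight.

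1. **Section 5.3 compares mean days, not a rate.** If follow-up is 24 weeks against six months, the shorter window lowers the follow-up total by a factor of 168/182 = 0.92. The three main scenarios then give raw ratios of 0.98, 1.04 and 1.10. This stands. A reader might infer that absence is bound to appear to rise; the documents do not support that.
2. **The size rests on assumed rates.** This also stands. If long spells are rare, the effect is about 2%. Non-response by nurses who are off sick, and regression to the mean if nurses volunteer after a bad spell, can shrink or reverse the net change. These are separate biases; an accidental offset does not make the comparison valid.
3. **The effect is easily overstated.** A reader might infer that the exclusion empties the pre-study window of long spells, or that a false finding of harm is likely. Neither follows. Spells that ended before recruitment remain in the window, and a significant spurious rise has a probability of only 3% to 12%.
4. **The analysis is exploratory and uncontrolled.** Hypotheses A to C do not concern absence, and the lack of a concurrent control is the larger weakness. This limits the severity. It does not remove the point, because the protocol describes no other analysis for this secondary objective and does not mention the selection.

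It is also fair to object to making nurses in service at week 40 the main figure. That conditions on a post-intervention state that is itself the outcome, and it sits badly with the intention-to-treat principle in 5.2. It is acceptable only as a sensitivity analysis.

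**Conclusion.** The concern holds as a minor point. The entry rule and the comparison in 5.3 together bias the before-after change in absence towards an increase. Under stationary absence of 5% of days and no intervention effect, the per-day excess is about 2% with short spells only and about 6% to 19% with long spells averaging 30 to 60 days. These sizes depend on rates that the protocol does not give; the direction of the selection effect does not. The direction of the net observed change is not assured, because window length, non-response and regression to the mean can act the other way.

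The practical harm is a masked or distorted reduction more than a false significant rise. The primary comparison of burnout scores at week 8 is untouched.

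**What to change.** In 5.3:

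1. Count absence over windows of equal length, for example the 24 weeks before week 0 and weeks 16 to 40, or as days per week at risk. This removes the length difference only.
2. Report the pooled before-after change as descriptive. State that excluding nurses on sick leave at recruitment biases it towards an increase, so that neither a rise nor an absence of change is read as evidence that the intervention does not reduce absence.
3. Beside the all-participants figure, and not in place of it, show the change among nurses in active service at week 40 as a sensitivity analysis. State that it conditions on a post-intervention state and leaves a small bias the other way (null ratios of 0.97 to 1.00 in the main scenarios, 0.92 in the extreme one).
4. Where absence reported at week 8 allows, also show the randomised between-group comparison for weeks 0 to 8. The exclusion applies equally to both groups there.

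The cost is one survey item at week 40, a change of recall period if 24-week windows are chosen, a little extra analysis, and a less conclusive absence result. Eight weeks is also a short period in which to observe absence, so the randomised comparison will be imprecise.
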